### 3.2.3

#### **Protocol Deviations**

Protocol deviations will be recorded and will capture the date of deviation, associated study visit, and type of deviation. Types of deviations are as follows:

- Consent procedures
- Inclusion/exclusion criteria
- Study procedures
- Serious adverse event / unanticipated adverse device effect (SAE/UADE) reporting
- Randomization procedures
- Visit schedule / window
- Other (site will be requested to specify)

### 3.3 *Evaluation Parameters*

### Time of Operative Phases

The time of the following pre-operative, operative and sterilization phases will be recorded (hh:mm:ss):

1. Surgery Room Preparation and Clean-up Phase
  - a. Instrument preparation for surgery from stock to Operative Room (OR)
  - b. Surgical table preparation
  - c. Instrument collection after surgery for sterilization
2. Intra-operative Phase
  - a. Patient OR time
  - b. Skin-to-skin time
  - c. Femoral and tibial resection times
  - d. Tourniquet time
3. Sterilization Phase
  - a. Instrument transportation to the sterilization unit
  - b. Instrument reception
  - c. Instrument cleaning before sterilization
  - d. Instrument decontamination before sterilization
  - e. Instrument sterilization
  - f. Instrument collection after sterilization
  - g. Instrument transportation to stock

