### **1.2 Study Treatment**

The GMK single-use (Efficiency) instruments are made of medical-grade composite technopolymers that give high fatigue and abrasion resistance in addition to form versatility. The single-use instruments are shipped from the manufacturer in pre-sterilized packaging, eliminating the need to use the hospital Central-Sterile processing equipment. The reproducible sterility may potentially reduce the infection risk.

---

 Losina E, *et al.* Cost-effectiveness of Total Knee Arthroplasty in the United States: Patient Risk and Hospital Volume. *Arch Intern Med* (2009); 169(2):1113-1122.

 Mont MA, *et al.* Single-Use Instruments, Cutting Blocks, and Trials Increase Efficiency in the Operating Room During Total Knee Arthroplasty: A Prospective Comparison of Navigated and Non-Navigated Cases. *J Arthroplasty* (2013); 28(7):1135-1140.

 Siegel Gw, *et al.* Cost Analysis and Surgical Site Infection Rates in Total Knee Arthroplasty Comparing Traditional vs. Single-Use Instrumentation. *J Arthroplasty* (2015); 30: 2271-2274

 Lachiewicz, PF, Henderson, RA: Patient-specific Instruments for Total Knee Arthroplasty. *J Am Acad Orthop Surg*, 2013; 21:513-518.

MyKnee® patient-specific cutting blocks allow the surgeon to realize his pre-operative 3D planning, based on CT or MRI images of the patient's knee. The blocks are created based on the individual patient's anatomy, his/her mechanical axis, and the surgeon's preferred reconstruction goals. The innovative concept combines the following features giving potential benefits to both the surgeon and the patient:

- Accurate bony cuts and therefore implant positioning
- No intramedullary canal violation
- Up to 60% reduction of surgical steps for bone resection and related time
- Up to 66% reduction of time and cost in washing, assembling and sterilization procedures
- Interactive 3D web planning

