#### **Primary Objective:**

- To compare the time-saving parameters associated with the two procedures with respect to parameters such as OR preparation time, intra-operative time (OR efficiency), OR clean-up time and sterilization costs.

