#### **Secondary Objectives:**

To compare the following surgical and clinical outcomes between the two study groups

- To compare correction of alignment after total knee replacement via long standing AP hip-knee-ankle x-rays.
- To compare the accuracy of tibial slope angle on a lateral knee x-ray
- To compare the number of trays sent to sterilization
- To compare the volume of estimated blood loss during the procedure
- To compare the drop in post-operative (day 1) hemoglobin and total volume of transfusions (allogeneic and/or autologous)
- To compare the occurrence of adverse events
- To compare the waste weight at the end of each surgery, considering separately those recyclable and those not recyclable.
- To compare the rate of intraoperative and post-operative complications
- To compare the rate of successful use of MyKnee® cutting blocks (i.e. the incidence of surgical cases where the surgeon did not need to abort the use of MyKnee intra-operatively and default to the use of standard cutting blocks).

The cost-per-minute value based on hospital estimates will be used to calculate an overall cost-savings total.

## 2

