### **STUDY DESIGN**

The study is a multi-center, prospective, randomized study comparing surgical and economic parameters of Total Knee Replacement performed with single-use Efficiency instruments with patient-specific technique (MyKnee®) versus traditional metal instruments with conventional surgical technique. The objective is to evaluate the impact of single-use instrumentation versus traditional metal instruments in reducing overall surgical costs and improving mechanical axis alignment. The timing of routine surgical phases will be measured, including the pre-operative preparation time, intra-operative phase, OR clean-up time and sterilization phase in 300 adult patients undergoing total knee replacement. AP and lateral x-rays will be utilized to assess the implant's mechanical axis alignment and tibial slope after discharge to the completion of the 6 week visit. Additionally, other parameters will be recorded including blood loss, post-op day 1 hemoglobin drop, adverse events, number of trays sent to sterilization, and total waste weight at the end of each procedure, considering separately those recyclable and those not recyclable. To ensure that the minimum of 300 patients is met, 342 patients will be randomized into two treatment cohorts in a 2:1 ratio.

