### Additional Operative Parameters

1. Estimated blood loss (cc)
2. Drop in post-operative hemoglobin (measured at Day 1 or discharge if patient does not stay overnight)
3. Total volume of transfusions (allogeneic and/or autologous)
4. Number of trays sent to sterilization
5. Waste weight at the end of each surgery; recyclable and non-recyclable (grams)

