#### **4.1 Data Analysis**

The objectives of this study are outlined in Section 1.3. For purposes of this study, economic outcomes of interest include the peri-operative time, intra-operative time (OR efficiency), and sterilization times as quantitative values. These outcomes will be subsequently used in comparative cost analyses. The secondary objectives are to assess the accuracy of mechanical axis alignment and posterior tibial slope after total knee replacement, additional operative parameters, and adverse events.

Descriptive statistics, specifically means will be used to summarize the peri-operative, intra-operative and sterilization time data.

The primary objective will be met by comparing mean values of each of the time-saving parameters. The null hypotheses of no differences in mean values between re-usable and single-use devices will be tested using separate t-tests for two independent groups for each endpoint. A p-value of less than 0.05 will be considered significant for each endpoint. Endpoints with statistically significant differences are expected to contribute to expected cost differences to be determined in subsequent analyses.

Descriptive analyses as well as similar two-sample comparisons will be used to evaluate secondary measures.

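### OR clean-up time, part of the primary objective, is timed only for instruments going to sterilization, so it covers different work in the two arms

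*Combined protocol and SAP*

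**What the plan says.** The primary objective in Section 1.3 compares the arms on "OR preparation time, intra-operative time (OR efficiency), OR clean-up time and sterilization costs". Section 2 repeats that clean-up time will be measured.

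Section 3.3 holds the only list of timed steps. Its first phase, "Surgery Room Preparation and Clean-up Phase", has three items. Items 1a and 1b are preparation. The only clean-up item is 1c, "Instrument collection after surgery for sterilization". No start or stop event is given for it.

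Section 1.2 describes the Group A instruments as supplied pre-sterilized, "eliminating the need to use the hospital Central-Sterile processing equipment". Waste is recorded by weight in grams; Section 2 refers to "total waste weight at the end of each procedure, considering separately those recyclable and those not recyclable". No time is attached to disposing of it.

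Section 4.1 tests the time parameters by "separate t-tests for two independent groups for each endpoint", each at 0.05, and expects the significant ones to contribute to the cost differences. Section 1.3 adds: "The cost-per-minute value based on hospital estimates will be used to calculate an overall cost-savings total".

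**The concern.** Item 1c is defined by where the instruments go next, and that is the feature that separates the arms. A metal set is collected for sterilization; a single-use set is not. A site that follows the item literally times the clearing of Group B's instruments. In Group A it times only the trays that remain reusable.

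If handling the single-use set after surgery takes longer than the waste handling that Group B also needs, the extra minutes are left out of the comparison. The error would favour single-use instruments. It would enter one of the primary tests and then, through the cost-per-minute conversion, the cost-savings total. A shorter recorded time could then reflect what was timed rather than less work in the room.

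**Working it through.** **1. Can another timed item pick up the missing work?**

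| Section 3.3 list | What it covers | Discarding the single-use set? |
|---|---|---|
| 1a, 1b | Preparation before surgery | No |
| 1c | Collection for sterilization | Not as worded |
| 2a to 2d | Patient OR, skin-to-skin, resection and tourniquet times | No, these are intra-operative |
| 3a to 3g | Steps for instruments sent to sterilization | No |
| Additional parameters | Waste weight, number of trays | Not times |

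The visit schedule in Section 3.4 has timing rows for the pre-operative, intra-operative and sterilization phases only. It has no row for clean-up or disposal.

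**2. The plan's own figures.** The Instrument Cleanup row (combined) of the Section 4.2 table gives means of 20.50 and 16.75, difference 3.752, SD 9.72 and effect size 0.386. The table prints no unit; I read minutes.

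- Effect size: 3.752 / 9.72 = 0.386, as stated.
- N at 80% power, two-sided 0.05, 2:1: control n = (1.960 + 0.842)² × (1 + 1/2) / 0.386² = 79.0, rounded up to 80, so the total is 240, as stated. At 85% and 90% the same method gives 273 and 318, against 275 and 320 stated.
- Overall N is driven by set-up time (2.985 / 8.66 = 0.345), which gives 300; 300 × 1.14 = 342. This also reproduces, so the sample size is not affected by this point.

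In the same row single-use clean-up took 16.75 / 20.50 = 82% of the traditional time. In the planning data, clearing up after single-use cases was therefore not negligible. The documents do not say how the cited study defined clean-up.

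**3. Illustration of the effect on the test.** Let m be Group A's untimed disposal time per case in excess of Group B's. The documents give no value for m, so the values below are assumptions. Suppose that full clean-up times are equal in the two arms. The recorded 1c times then differ by m.

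- SE = 9.72 × √(1/114 + 1/228) = 1.115
- Smallest significant difference = 1.960 × 1.115 = 2.19 minutes
- P(reject) = Φ(m/SE − 1.960) + Φ(−m/SE − 1.960)

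| m (assumed, minutes) | m/SE | P(reject) |
|---|---|---|
| 0 | 0 | 5% |
| 0.5 | 0.45 | 7% |
| 1 | 0.90 | 15% |
| 2 | 1.79 | 43% |

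This uses the normal approximation and takes the planning SD to apply to the recorded interval.

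**The case against.** The other side has several fair points.

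- **The definition is loose.** Item 1c sits under a phase titled as clean-up, Section 2 promises clean-up time, and no start or stop is given. A site could time the clearing of the whole table in both arms, and the case report forms are not among the documents. This stands: a reader might infer that Group A's disposal minutes are certain to be missed, and the text does not show that. It shows only that no item asks for them. If sites differ in how they read 1c, the endpoint is inconsistent across sites instead.
- **Both arms produce waste.** Recyclable and non-recyclable waste is weighed after every procedure. This stands: only Group A's net excess over Group B can bias the comparison, not its whole disposal time. Trays sent to sterilization are also counted in both groups, so 1c need not be empty in Group A.
- **The share of the planned saving that is artefact cannot be given.** It is tempting to set a few assumed minutes against the planned 3.752. If that figure is already inflated, the share is m/3.752, or 27% to 80% for m of 1 to 3. If it is the true difference, the share is m/(3.752 + m), or 21% to 44%. Choosing between these needs the cited study's definition of clean-up, and nothing in the documents supports 1 to 3 minutes. I draw no conclusion from either range.
- **Clean-up is one of several primary parameters** and does not set the sample size. This also stands, and it limits the severity.

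None of this makes the interval comparable. As written, 1c is tied to a destination that the single-use set does not have.

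**Conclusion.** The point holds as a defect of definition: a component of the primary objective is specified by a step that covers different work in the two arms, and no other timed item fills the gap. The direction is conditional. If Group A has a net excess of untimed disposal work, the comparison favours single-use instruments. A reader might go further and say that the clean-up saving is biased by a known amount. The documents do not support that, because they give no disposal times, do not describe how the single-use set is discarded, and leave sites free to include disposal.

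The rejection rates of about 7%, 15% and 43% show how sensitive the test would be to an assumed net excess of 0.5, 1 or 2 minutes. They do not estimate the actual bias. This should be fixed, because the endpoint enters both a primary test and the cost total, but the rest of the primary comparison and the sample size do not depend on it.

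**What to change.** Define OR clean-up time with one start and one stop that apply to both arms:

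- **Start:** patient out of the room. Starting at wound closure could overlap Patient OR time (item 2a) and count the same minutes twice in the cost calculation.
- **Stop:** all instruments and their packaging, reusable and disposable, cleared from the OR.
- **Waste:** include separation of recyclable from non-recyclable waste only where it is routine practice. Exclude weighing or sorting done only for the study.

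Use this interval as OR clean-up time in the primary comparison and in the cost calculation. Keep item 1c as a descriptive sub-interval.

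The cost is a short amendment and a small change to a timing form that staff already complete. The measured saving may be smaller, and the SD of the wider interval may differ from the planning value of 9.72, so power for this endpoint should be looked at again. Minutes that were not timed cannot be recovered afterwards, so the change helps only the procedures timed under it.

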### Additional Operative Parameters

1. Estimated blood loss (cc)
2. Drop in post-operative hemoglobin (measured at Day 1 or discharge if patient does not stay overnight)
3. Total volume of transfusions (allogeneic and/or autologous)
4. Number of trays sent to sterilization
5. Waste weight at the end of each surgery; recyclable and non-recyclable (grams)

### Radiographic Parameters

Each subject will undergo the following radiographic assessments pre-operatively and at 6 weeks post-operatively.

- Long standing (hip to ankle) AP x-ray to assess the mechanical axis alignment
- Standard lateral x-ray to assess tibial posterior slope

Subjects randomized to Group A (Efficiency/MyKnee®) will also undergo a preoperative CT or MRI.

Accuracy will be determined by the difference between the final position on the post-operative x-rays and the surgeon's intended position (usually 0 degrees of mechanical axis on AP, and recreation of tibial slope on the lateral x-ray).

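### Alignment and slope accuracy is defined only as a difference from target; read literally, the planned comparison tests mean signed error (bias), not closeness to the intended angle

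*Combined protocol and SAP*

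**What the plan says.** The combined protocol and SAP defines accuracy once, in Section 3.3 under Radiographic Parameters: "Accuracy will be determined by the difference between the final position on the post-operative x-rays" and the position the surgeon intended. The target is described as "usually 0 degrees of mechanical axis on AP, and recreation of tibial slope on the lateral x-ray". Nothing there, or elsewhere in the document, mentions an absolute value, a squared error, a measure of spread or a tolerance band.

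Section 4.1 (Data Analysis) lists among the secondary objectives to "assess the accuracy of mechanical axis alignment and posterior tibial slope after total knee replacement". The time endpoints are to be "tested using separate t-tests for two independent groups for each endpoint", each at 0.05. For the rest, the plan says: "Descriptive analyses as well as similar two-sample comparisons will be used to evaluate secondary measures".

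The Secondary Objectives in Section 1.3 use different words for the two angles: "To compare correction of alignment after total knee replacement via long standing AP hip-knee-ankle x-rays" for alignment and "To compare the accuracy of tibial slope angle on a lateral knee x-ray" for slope. Section 4.1 refers back to Section 1.3 and then uses accuracy for both. Section 2 (Study Design) gives the topic prominence by naming "reducing overall surgical costs and improving mechanical axis alignment" in the study objective.

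**The concern.** An angular error can fall on either side of the target; the exclusion criteria themselves speak of varus or valgus deformity. If accuracy is the plain difference, achieved minus intended, its mean is the average bias of an arm. An arm with large errors in both directions can have a mean of zero. A t-test of that mean asks whether the arms are biased by different amounts. It does not ask which arm lands closer to the intended angle, and the word accuracy suggests the second question.

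Two wrong conclusions become possible. A real gain in consistency with patient-matched blocks could go undetected. Conversely, two arms equally far from target on average, but erring in opposite directions, could be reported as differing in accuracy. Because the plan does not fix the metric, the choice could also be made after the data are seen, and one choice may be significant where the other is not.

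**Working it through.** **The plan's own figure.** Section 4.2 sizes the trial on time endpoints. Set-up time governs: d = 2.985, SD = 8.66, d/SD = 0.345. At 2:1, two-sided 0.05 and 80% power, the smaller arm needs 1.5 × (1.960 + 0.842)² / 0.345² ≈ 99.1 patients, so 100, giving 200:100 = 300. Then 300 × 1.14 = 342, or 228:114. This reproduces the plan. No size or power is stated for alignment or slope.

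**Inputs for the illustration.** The arm sizes (A = 228, B = 114) and alpha 0.05 are from Sections 4.1 and 4.2; a two-sided test is assumed. The documents give no SD or offset for angular error, so every SD and mean below is an assumption, as is normality.

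**Formulas.**
- Signed error: SE = √(σA²/228 + σB²/114), and power ≈ Φ(|μB − μA|/SE − 1.96).
- Absolute error when the arm is on target: mean = 0.798σ, SD = 0.603σ.
- Absolute error with offset μ: mean m = 0.798σ·exp(−μ²/2σ²) + μ[1 − 2Φ(−μ/σ)], variance = μ² + σ² − m².

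**Case 1: both arms on target, SD 2 (A) and 3 (B).**
- Signed: the true mean difference is 0, so a Welch test rejects at about 5%. A pooled test uses variance (227×4 + 113×9)/340 = 5.66, hence SE √(5.66 × (1/228 + 1/114)) = 0.273, while the true SE is √(4/228 + 9/114) = 0.311. Its effective cut-off is 1.96 × 0.273/0.311 = 1.72, a rejection rate of about 8.5%. That excess comes from unequal variances in unequal arms; it is not power.
- Absolute: means 1.60 and 2.39, difference 0.80. SE = √(1.206²/228 + 1.808²/114) = 0.187. Ratio 4.26, power about 99%.

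**Case 2: both on target, SD 2.5 and 3.** Absolute means 1.99 and 2.39, difference 0.40, SE 0.197, ratio 2.03, power about 53%. The signed test stays near 5%.

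**Case 3: offsets −0.5 and +0.5, SD 2 in both.** Mean absolute error is 1.65 in both arms, so the arms are equally accurate. Signed: SE = 2 × √(1/228 + 1/114) = 0.229, ratio 1/0.229 = 4.36, power about 99%. Absolute: about 5%.

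**Case 4: 1-degree offset in arm B only, SD 2 in both.** Signed: about 99%, as in Case 3. Absolute: means 1.60 and 1.79, difference 0.195, SE = √(1.206²/228 + 1.339²/114) = 0.149, ratio 1.31, power about 26%.

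**Simulation** (20,000 trials per case; rejection in %, Welch/pooled):

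| Case | Signed | Absolute |
|---|---|---|
| 1. On target, SD 2 vs 3 | 4.7 / 8.1 | 99.4 / 99.6 |
| 2. On target, SD 2.5 vs 3 | 4.9 / 6.5 | 52.5 / 56.9 |
| 3. −0.5 vs +0.5, SD 2 | 99.1 / 99.1 | 5.1 / 5.1 |
| 4. 0 vs 1, SD 2 | 99.1 / 99.1 | 24.5 / 27.5 |

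The simulation agrees with the formulas. At 200:100 the pattern is the same: Case 2 absolute 46.7 / 51.8, Case 4 absolute 21.8 / 25.0.

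**The case against.** **Accuracy may already mean absolute deviation.** Accuracy against a target ordinarily means closeness, and a difference between two positions is silent on sign. A reader might infer that the plan commits to a signed test. It does not: the text permits either reading. What stands is that the written operation is a difference, and nothing tells the analyst to drop the sign.

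**A t-test for these endpoints is inferred.** The secondary measures include event rates and the success rate of the cutting blocks, so the phrase about similar comparisons cannot mean t-tests throughout. Nor does anything prevent SDs being reported for the angles. Still, for a continuous angle the only comparison described before that phrase is a t-test of means.

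**The objectives are linked.** A reader might infer that correction in Section 1.3 and accuracy in Section 4.1 are unconnected endpoints. Section 4.1 refers back to Section 1.3, so they are connected. The wording is loose, and correction could also be taken as a pre-to-post change, but no passage says that.

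**Absolute deviation is not always the more sensitive metric.** This is correct. In Case 4 it has about a quarter of the power of the signed test, and in Case 2 it reaches only about 53 to 57%. The figures show that the metric must be stated and both aspects reported; they do not show that one metric wins everywhere.

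**These are secondary endpoints without a power claim.** Also correct, and it limits the weight of the point.

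**Conclusion.** The point holds in a limited form. The plan's only definition of accuracy, followed literally, leads to a comparison of mean signed error. That comparison measures bias, is nearly blind to a difference in scatter, and can declare a difference between arms equally close to target. The absolute reading is open but unstated.

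The direction of this conclusion does not depend on the assumed values; its size does. With assumed normal errors at 228:114, the choice of metric moves the rejection rate from about 5% (8 to 9% pooled) to 99% in Case 1, and from 99% to 5% in Case 3. These cases were chosen to show the contrast and are not forecasts for this trial.

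A reader might infer that the trial's main result or its size is in doubt. The documents do not support that: the primary objective concerns times and sterilization costs, and N = 300 and 342 reproduce from the time data. The matter should be settled before analysis because alignment is named in the study objective.

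**What to change.** 1. In Radiographic Parameters (Section 3.3) and Section 4.1, define accuracy as |achieved − intended| in degrees, separately for mechanical axis and tibial slope. Compare its mean between arms with a 95% CI.
2. Report the signed mean difference with its 95% CI as bias, and the SD of the errors in each arm as scatter.
3. Use the surgeon's intended angle for each patient as the target, since the values in Section 3.3 are described only as usual. Confirm that this angle is recorded for every patient in both arms: the visit lists and schedule in Section 3.4 do not name it, and three-dimensional planning is described only for Group A.
4. Use one wording for the alignment objective in Sections 1.3 and 4.1. If correction is meant as a pre-to-post change, list it as its own measure.
5. As a separate step for precision, adjust these comparisons for site, because randomization is done within site (Section 3.2.2), and for the pre-operative angle already collected at Visit 1. This does not resolve the signed-or-absolute question, but it needs no new data.

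The cost is a few sentences, a little more analysis and, if the intended angle is not yet captured, one data item for each of the two angles. The x-rays are already scheduled. The drawback is lower sensitivity to a pure offset in one arm (about 24 to 28% against 99% for 1 degree with SD 2), which is why the signed mean stays alongside.
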